#### *5.2.4.1.1 Hypothesis Statement – Primary Effectiveness*

The null hypothesis states the percentage of all implanted subjects that are Treatment Responders at 6-months is less than 50%. Rejection of the null hypothesis indicates that the observed data support the alternative hypothesis that the percentage of Treatment Responders is greater than 50%.

Therefore, the hypotheses to be tested are:

$$H_0: \pi \leq 0.5$$

$$H_a: \pi > 0.5$$

where  $\pi$  is the percentage of all implanted subjects that are Treatment Responders at 6 months.

#### *5.2.4.2 Secondary effectiveness endpoints*

A total of six (6) secondary endpoints are planned, five (5) of which are in all implanted subjects, and one (1) in Trial Responder subjects. The analysis of all secondary effectiveness endpoints will be based on all available data. Details on handling of missing data are provided in Section 5.2.4.6.

##### *5.2.4.2.1 Responder Rate in Trial Responder Subjects at 6-Month Follow-Up*

This secondary effectiveness endpoint is that the proportion of Trial Responder subjects that are Treatment Responders is greater than 50% at 6-months post-activation. The null hypothesis states the percentage of Trial Responders that are Treatment Responders at 6-months is less than 50%. Rejection of the null hypothesis indicates that the observed data support the alternative hypothesis that the percentage of Trial Responders that are Treatment Responders is greater than 50%.

Therefore, the hypotheses to be tested are:

$$H_0: \pi \leq 0.5$$

$$H_a: \pi > 0.5$$

where  $\pi$  is the percentage of Trial Responder subjects that are Treatment Responders at 6-months.

#### *5.2.4.2.3 Reduction from Baseline in Average Daily Number of Urgency Leaks*

The null hypothesis states that the reduction from Baseline in the average number of daily leaks with urgency is greater than 0 at 6-month follow-up visit for all implanted subjects. Rejection of the null hypothesis indicates that the observed data support the alternative hypothesis that the reduction from baseline in this secondary effectiveness endpoint is no more than 0. The hypotheses to be tested are:

$$H_0: \mu \leq 0$$

$$H_a: \mu > 0$$

where  $\mu$  is the reduction from Baseline in the average number of daily urgency leaks at 6-months in all implanted subjects.

#### *5.2.4.2.4 Reduction from Baseline in Average Daily Number of Large Leaks with Urgency*

The null hypothesis states that the reduction from Baseline in the average number of daily large leaks associated with urgency is greater than 0 at 6-month follow-up visit in all implanted subjects. Rejection of the null hypothesis indicates that the observed data support the alternative hypothesis that the reduction from baseline in this secondary effectiveness endpoint is no more than 0. The hypotheses to be tested are:

$$H_0: \mu \leq 0$$

$$H_a: \mu > 0$$

where  $\mu$  is the reduction from Baseline in the average number of daily large leaks with urgency at 6-months in all implanted subjects.

#### *5.2.4.2.5 Reduction from Baseline in Average Daily Urgency*

The null hypothesis states that the reduction from Baseline in the average daily urgency is greater than 0 at 6-month follow-up visit for all implanted subjects. Rejection of the null hypothesis indicates that the observed data support the alternative hypothesis that the reduction from baseline in this secondary effectiveness endpoint is no more than 0. The hypotheses to be tested are:

$$H_0: \mu \leq 0$$

$$H_a: \mu > 0$$

where  $\mu$  is the reduction from Baseline in the average daily urgency at 6-months in all implanted subjects.

#### *5.2.4.2.6 Improvement from Baseline in Average Daily Number of Voids*

The null hypothesis states that the improvement from Baseline in the average number of daily voids is greater than 0 at 6-month follow-up visit for all implanted subjects who had at least eight (8) average daily voids at Baseline. Rejection of the null hypothesis indicates that the observed data support the alternative hypothesis that the improvement from baseline in this secondary effectiveness endpoint is no more than 0. The hypotheses to be tested are:

$$H_0: \mu \leq 0$$

$$H_a: \mu > 0$$

where  $\mu$  is the improvement from Baseline in the average number of daily voids at 6-months in all implanted subjects who had at least eight (8) average daily voids at Baseline.

#### *5.2.4.3 Analysis of Secondary Effectiveness Endpoints*

The secondary effectiveness endpoints that are collected as continuous measures will be tested for significance based on two-sided t-test or paired t-test, as appropriate. If the underlying data distribution is found to be non-normal, a non-parametric method (e.g., Wilcoxon signed-rank test) may be employed. The secondary effectiveness endpoints that are collected as binomial measures will be tested for significance based on a binomial test (such as Fisher's exact test).

After evaluation of the primary endpoint hypothesis, secondary effectiveness endpoints will be evaluated in a serial manner. To control for family-wise error rate, Holm's correction for multiple testing will be utilized. If the null hypothesis of the primary effectiveness endpoint is not rejected, no further testing of any of the other endpoints will occur. If the null hypothesis of the primary endpoint is rejected, the significance testing of the secondary endpoints can commence.

To control for a family-wise error rate among the six secondary effectiveness endpoints, Holm's correction will be implemented with a total  $\alpha=5\%$ . To account for an early look analysis performed on the 6-month data, Axonics plans to allocate no more than  $\alpha=2.5\%$  for the early analysis. The final analysis will be allocated alpha of 2.5% along with any remaining alpha from the early analysis.

Therefore, for each analysis (early and final) the unadjusted p-values from the testing of the six secondary endpoints will be ordered from smallest to largest. For the early analysis, the smallest p-value will be compared to the cut-off value of  $0.025/6=0.0041$ , the next one being compared to  $0.025/5=0.005$ , the next one being compared to  $0.025/4=0.00625$  and so forth. For the final analysis, any alpha remaining from early analysis will be added to 0.025 and will be used for comparing cut off values. The null hypotheses will be rejected for the tests where the unadjusted p-value is smaller than the corresponding cut-off value, and for all sequentially preceding hypothesis tests.

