### *5.2.4 Analysis methods*

#### *5.2.4.1 Primary Endpoint*

The primary effectiveness endpoint is that the proportion of all implanted subjects that are Treatment Responders is greater than 50% at 6-months post-activation. If the proportion of Treatment Responders is statistically greater than 50%, the study will be considered to be a success.

As mentioned above, a secondary endpoint analysis will also be conducted in subjects who are "Trial Responders" to allow for a direct comparison to the published SNM literature where analysis at follow-up visits are performed only in trial responders i.e. subjects that have  $\geq 50\%$  improvement in

symptoms after a one-month trial with an external stimulator.

The primary endpoint will be tested for significance based on a one-sided binomial test (such as Fisher's exact test) at a 2.1% significance level to account for two additional early looks as detailed in the Statistical Analysis Plan.

The primary safety endpoint of the study is the rate of adverse events (AEs) through 6-months.

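### The rejection sentence in section 5.2.4.3 reads most plainly as a step-up rule, although the plan names Holm's step-down procedure; separately, five secondary nulls are worded as the reverse of their own formulas

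*Combined protocol and SAP*

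**What the plan says.** Section 5.2.4.3 opens secondary testing only after the primary null has been rejected: "If the null hypothesis of the primary effectiveness endpoint is not rejected, no further testing of any of the other endpoints will occur". It then says that "secondary effectiveness endpoints will be evaluated in a serial manner" and that "Holm's correction for multiple testing will be utilized". The six p-values are ordered from smallest to largest. At the early analysis they are compared with 0.025/6, 0.025/5, 0.025/4 and so on. The paragraph closes by stating that nulls are "rejected for the tests where the unadjusted p-value is smaller than the corresponding cut-off value, and for all sequentially preceding hypothesis tests". Nothing is said about stopping at the first p-value that misses its cut-off.

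Sections 5.2.4.2.2 to 5.2.4.2.6 each describe one continuous endpoint in words and then in symbols. In each, the words make a positive improvement or reduction the null, and say that rejection supports a change no larger than zero. The symbols are H0: μ ≤ 0 and Ha: μ > 0, with μ defined as the improvement or reduction. Section 5.2.4.2.1, on the responder rate in Trial Responders, is worded in the same direction as its formulas.

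On sidedness, section 5.2.4.3 has the continuous endpoints "tested for significance based on two-sided t-test or paired t-test, as appropriate". It gives no side for the binomial test in Trial Responders.

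**The concern.** Holm's procedure and a step-up procedure (Hochberg's) can use the same cut-offs and differ only in direction. Holm starts at the smallest p-value and stops at the first failure. Step-up finds the largest p-value that passes and rejects it together with every smaller one, including any that missed its own cut-off.

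The closing clause of section 5.2.4.3 adds nothing under Holm, because every earlier test must already have passed. It does work only if an earlier test that failed is rescued by a later one that passed, which is step-up. Two analysts following this section could therefore report different lists of successful secondary endpoints from one dataset. In a pivotal pre-market study those endpoints may support claims, so the rule should be settled in the text.

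The reversed wording is a smaller matter. Taken alone, the prose attaches the opposite conclusion to a rejection for five of the six secondary endpoints.

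**Working it through.** **1. The plan's cut-offs.** With m = 6 and total α = 0.025, cut-off k is α/(m − k + 1): 0.025/6 = 0.004167, 0.025/5 = 0.005, 0.025/4 = 0.00625, 0.025/3 = 0.00833, 0.025/2 = 0.0125 and 0.025/1 = 0.025. The plan's 0.005 and 0.00625 reproduce. Its 0.0041 is 0.004167 truncated, which is slightly conservative and immaterial.

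**2. The two readings on the same p-values.** These examples are constructed.

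| Ordered p-values | Total α | Holm rejects | Literal sentence rejects |
|---|---|---|---|
| 0.0045, 0.0049, four large | 0.025 | 0 | 2 |
| 0.0045, 0.0049, four large | 0.05 | 2 | 2 |
| 0.013, 0.014, 0.016, 0.018, 0.020, 0.024 | 0.025 | 0 | 6 |
| 0.013, 0.014, 0.016, 0.018, 0.020, 0.024 | 0.05 | 0 | 6 |

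First row: 0.0045 > 0.004167, so Holm stops at once. Since 0.0049 < 0.005, the literal sentence rejects the second test and the one before it. Third row: 0.013 > 0.004167 stops Holm, while 0.024 < 0.025 passes the last cut-off and carries all six. In the fourth row the first and last cut-offs are 0.00833 and 0.05, with the same outcome.

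**3. How often the readings differ.** The documents give no secondary effect sizes, so these are assumptions: six z-statistics with equal mean and equal correlation of 0.3 or 0.6, two-sided p-values, total 0.025, 200,000 replicates per setting.

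| Mean z | Analyses in which the rules disagree |
|---|---|
| 2 to 4 | 1.5% to 5.0% |
| 5 | 0.1% to 0.2% |
| 6 | about 0% |

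At mean z of 2 to 4, a disagreement means on average 2.4 to 3.0 more endpoints declared by the literal sentence.

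**4. Family-wise error, all six nulls true.** Two-sided p-values, one analysis, 1,000,000 replicates:

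| Correlation | Holm, 0.025 | Step-up, 0.025 | Holm, 0.05 | Step-up, 0.05 |
|---|---|---|---|---|
| 0 | 0.0248 | 0.0248 | 0.0488 | 0.0489 |
| 0.3 | 0.0239 | 0.0239 | 0.0460 | 0.0461 |
| 0.6 | 0.0195 | 0.0197 | 0.0377 | 0.0380 |
| 0.9 | 0.0112 | 0.0123 | 0.0213 | 0.0244 |

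Neither rule exceeds its level. Across an early and a final analysis at 0.025 each (400,000 replicates, correlation 0 to 0.9, information fraction 0.4 or 0.7), the step-up reading gives 2.0% to 4.6% and Holm 1.8% to 4.6%, against the stated 5%. The difference in guarantee appears only under arbitrary dependence. There the mathematical maximum with all six nulls true is 0.025 for Holm and 0.0506 for step-up at total 0.025, and 0.050 against 0.101 at total 0.05.

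**5. Words against formulas.**

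| Section | Null in words | Null in symbols | Agree? |
|---|---|---|---|
| 5.2.4.2.1 Trial Responder rate | below 50% | π ≤ 0.5 | yes, apart from equality |
| 5.2.4.2.2 ICIQ-OABqol | improvement above 0 | μ ≤ 0 | reversed |
| 5.2.4.2.3 urgency leaks | reduction above 0 | μ ≤ 0 | reversed |
| 5.2.4.2.4 large urgency leaks | reduction above 0 | μ ≤ 0 | reversed |
| 5.2.4.2.5 urgency | reduction above 0 | μ ≤ 0 | reversed |
| 5.2.4.2.6 voids | improvement above 0 | μ ≤ 0 | reversed |

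**6. Sidedness of the binomial test.** If the 80–85% trial success rate in section 5.2.2 applied to 116 implanted subjects, there would be 93 to 99 Trial Responders (116 × 0.80 = 92.8; 116 × 0.85 = 98.6). Against 50% at 0.00417, the exact test needs 60 responders one-sided or 61 two-sided at n = 93, and 64 or 65 at n = 99. At an assumed true rate of 80%, power exceeds 99.9% in every case.

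**The case against.** The context points to Holm. The section names the procedure twice and calls the testing serial. The closing clause can also be read as requiring the p-value to be below its cut-off at this step and at all earlier ones. That reading is available and may well be what was meant. It does not remove the defect, because the clause more naturally extends rejection backwards and no stopping rule corrects it.

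The practical effect is modest. The 0-against-6 case is constructed, the effect sizes are assumed, and disagreement fades as effects grow. All of this stands and limits the weight of the point.

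The reversed prose is close to clerical. Each of the five sections presents the symbols as the hypotheses to be tested, defines μ, and carries a heading in the same direction. A reader might infer that five tests would be run the wrong way round. The documents do not support that.

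A reader might also see a conflict between the primary endpoint's level being set "to account for two additional early looks as detailed in the Statistical Analysis Plan" and section 5.2.4.3 providing for one ("To account for an early look analysis performed on the 6-month data"). A look need not include 6-month data or secondary tests, and section 5.2.4.1 leaves the details to a separate statistical analysis plan that is not in the text reviewed. No contradiction is shown.

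Nor does "The final analysis will be allocated alpha of 2.5% along with any remaining alpha from the early analysis" open the door to spending beyond 5%. The section caps the early allocation at 2.5%, so what remains is naturally 2.5% less the amount allocated early. A one-line definition would help, but its absence is not an error.

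**Conclusion.** The point holds as an ambiguity in the secondary decision rule, together with a text error in five hypothesis statements. The plan names Holm, while its operative sentence most plainly describes step-up. The two can differ by as much as none against six endpoints in a constructed case. They differ in at most about 5% of analyses under the assumed equal effects and correlations of 0.3 to 0.6.

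A reader might infer that the step-up wording inflates the family-wise error rate. Under the non-negative correlations simulated it does not, and positive correlation is plausible for endpoints drawn largely from one diary. Only Holm, however, holds the level whatever the dependence. The primary endpoint and the study success criterion are unaffected. What is at stake is which secondary claims the plan supports.

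The sidedness of the six p-values is a consistency point only, worth one responder in the binomial test. The ambiguity and the reversed wording can be checked by reading the text; only the frequency and error-rate figures rest on assumptions.

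**What to change.** (a) Replace the last sentence of section 5.2.4.3 with: *Starting from the smallest p-value, a null hypothesis is rejected only if its p-value and all smaller p-values are below their cut-offs; testing stops at the first p-value that is not, and that hypothesis and all later ones are not rejected.*

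(b) In sections 5.2.4.2.2 to 5.2.4.2.6, swap the worded null and alternative so that they match H0: μ ≤ 0 and Ha: μ > 0.

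(c) As a minor addition, state that all six p-values are two-sided, and that a rejected test supports a claim of improvement only if the estimate lies in the direction of Ha. Direction should stay out of the stopping rule. Otherwise one strongly adverse endpoint, ordered first, would block five others that meet their cut-offs.

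(d) Optionally, define remaining alpha as 0.025 minus the alpha allocated to early secondary tests, so that early plus final never exceeds 0.05.

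No new data or added sample size are needed. The cost is that Holm's stopping rule may declare fewer secondary endpoints than the literal sentence would.

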#### *5.2.4.4 Control of Systematic Bias*

Several measures are incorporated into the study design to help minimize study bias as follows:

- 1) This is a multi-center trial to help ensure that investigator or site or subject enrollment bias is minimized. Selection of subjects will be made from the Investigator's usual subject load. Consecutively eligible subjects should be enrolled into the study.
- 2) This document specifies appropriate statistical methodology to ensure that bias is minimized.
- 3) Standardized and validated questionnaires will be used to collect data during the study. Although many of the data collected would be considered subjective in nature, the standardization and validation of these metrics helps to remove systematic bias introduction into the study data.

#### *5.2.4.5 Pooling Data across Centers*

Up to 20 sites will enroll subjects into the study. The analyses will be presented using data pooled across study centers. Comparability between study sites, and US and non-US sites, will be examined based on the primary endpoint of Treatment Responder rate. Summary statistic for the Treatment Responder rate will be calculated by site and geographical area. A formal assessment of the poolability of subjects across sites will be performed.

#### *5.2.4.6 Handling of Missing Data*

##### *5.2.4.6.1 Primary endpoint*

The analysis of the primary effectiveness endpoint will be based on all available data. The missing data for implanted subjects will also be included in the analysis, and imputed based on the circumstance of the missing data. The following missing data classes have been identified:

###### Missing not at Random (MNAR):

Subjects that are intraoperative screen failures or explanted or withdrawn due to adverse event(s) or lack of efficacy will be considered treatment failures and their baseline diary data will be used as the primary endpoint diary data.

###### Missing at random (MAR):

Primary endpoint data for subjects who are missing at random (e.g., missed visits, incomplete data capture, withdrawals not related to safety or efficacy of device, death, loss to follow-up) will be imputed and analyzed using a multi-stage multiple imputation technique as follows:

- **Preliminary step:** the following variables will be considered in the multiple imputation procedure:
  - Age
  - Gender
  - Secondary diagnoses (stress incontinence, urinary frequency, retention, fecal incontinence, other, none)
  - Years since diagnosis of UUI

- Average daily number of urgency leaks at Baseline, Month 1, 2 and 3 visits.
- **Step 1:** Given the likely arbitrary missing data pattern, Markov Chain Monte Carlo (MCMC) method will first be used to impute just enough missing values among the variables to create a monotone missing pattern as needed for the monotone logistic regression imputation in Step 2.
- **Step 2:** A logistic regression model will be used to impute the missing values for the binary primary endpoint at Month 6 based on the partially imputed datasets created in Step 1. 200 imputed datasets will be created.
- **Step 3:** Each of the 200 imputed datasets created in Step 2 will be analyzed separately using binomial proportion estimation for the primary effectiveness endpoint at Month 6 to obtain parameter estimates of proportion and standard error.
- **Step 4:** Results obtained in Step 3 will be combined using the usual Rubin's rules for combining the imputed samples to account for variability of different imputations. This allows for a valid hypothesis test of the primary endpoint.

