### *3.3.6 Treatment Responders/Non-responders*

A subject is considered a Treatment Responder if at a given follow-up visit they achieve 50% or greater reduction in the number of urgency leaks compared to baseline on the 72-hour diary.

A subject is considered a Treatment Non-responder if they have analyzable data at the follow-up visit, but did not meet the above criteria for Treatment Responder.

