### *5.2.2 Sample Size Justification*

The study sample size was initially determined considering that the primary endpoint analysis will be performed in the Trial Responders cohort. The sample size considerations using these assumptions is provided in detail in previous versions of the protocol (Rev A- Rev E).

Based on FDA input, the primary endpoint analysis cohort was changed to all implanted subjects. At this stage (rev F), all subjects have been enrolled and implanted. A justification for why the currently implanted number of subjects is a sufficient sample size is provided below:

The primary effectiveness endpoint hypothesis is that the proportion of all implanted subjects that are Treatment Responders at 6-months is greater than 50% (null proportion).

1. Previous literature on SNM for UUI treatment was used to estimate the expected success rate of all subjects receiving this treatment. These studies have shown approximately 80-85% of the subjects that receive an external trial proceed to a permanent SNM implant. Long-term (>6 month) clinical success is seen in approximately 80-85% of the subjects with permanent implant. Thus, of all subjects that received SNM therapy, approximately 65-70% are therapy responders at long term follow-up.
2. Assuming that the true proportion of Treatment Responders is 65%, one hundred and sixteen (116) implanted subjects at 6-months provides approximately 90% power to show that the percentage of Treatment Responders is greater than 50%, assuming a one-sided Type I error rate of 0.021. The one-sided Type I error rate of 0.021 is used to account for planned early look analyses (per the Statistical analysis plan).
3. Assuming an attrition rate of 20% between enrollment and the implant procedure due to screen failures and withdrawals, the total number of enrolled subjects will be capped at approximately one hundred and forty-five (145). Therefore, the study will continue to enroll subjects until either:
  - One-hundred and forty-five (145) patients are enrolled (“Enrollment Cap”), or

---

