#### *5.2.4.6.2 Secondary and Exploratory endpoints*

For secondary and exploratory endpoint analyses that use subject-reported outcomes/ questionnaires, missing data will be addressed by the specific scoring guideline provided by the questionnaires. In the cases where the response does not contribute to a score, no imputation will be performed. Subjects with missing or incomplete diaries at 6 months will be included in the secondary/exploratory endpoint analysis by using their Baseline diary data.

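### The primary-endpoint imputation ignores leaks already recorded in an incomplete Month 6 diary, so a proven non-responder can be imputed as a responder, and the rate is overstated if incompleteness is related to Month 6 leakage

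*Combined protocol and SAP*

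**What the plan says.** Section 3.3.6 defines a Treatment Responder by a "50% or greater reduction in the number of urgency leaks compared to baseline on the 72-hour diary". A Non-responder must have analyzable data at the visit; that term is not defined.

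Section 5.2.4.6.1 sorts missing primary-endpoint data into two classes. Failure is set by rule only for intraoperative screen failures and for explants or withdrawals caused by adverse events or lack of efficacy. The other class, "subjects who are missing at random (e.g., missed visits, incomplete data capture" and further reasons, goes to multiple imputation. A logistic model then fills in the binary Month 6 response in 200 datasets. The candidate variables are age, gender, secondary diagnoses, years since diagnosis, and average daily urgency leaks at Baseline and Months 1, 2 and 3. No Month 6 diary information is listed.

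For the other endpoints, Section 5.2.4.6.2 foresees the partial diary by name: "Subjects with missing or incomplete diaries at 6 months will be included", with the Baseline diary standing in. Section 5.2.4.7 adds a tipping-point analysis in which each missing value may be set either way.

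**The concern.** The endpoint is a count over 72 hours, and a count cannot fall as more hours are recorded. Leaks in a partial diary are therefore a lower bound on the full count. Once that bound passes half of the baseline count, non-response is settled whatever the missing hours hold. At the minimum qualifying baseline of 4 urgency leaks (Section 3.1), 3 recorded leaks are enough, because the reduction is then at most 25%.

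The plan treats this settled outcome as unknown. With a model probability of 0.65, such a subject is a responder in about 130 of the 200 datasets (0.65 × 200).

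What is at stake is the responder rate in a single-arm trial judged against a fixed 50% goal. The case to fear is a subject who did well to Month 3, then lost the effect, and kept only part of the Month 6 diary. Months 1 to 3 predict response; the recorded Month 6 hours show failure; the model sees only the former.

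**Working it through.** **1. The plan's own figure.** Section 5.2.2 states: "Assuming that the true proportion of Treatment Responders is 65%, one hundred and sixteen (116) implanted subjects at 6-months provides approximately 90% power", "assuming a one-sided Type I error rate of 0.021". By normal approximation with z = 2.0335:

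- standard error under the null: √(0.25/116) = 0.0464
- standard error at 65%: √(0.2275/116) = 0.0443
- power = Φ[(0.15 − 2.0335 × 0.0464)/0.0443] = 89.5%

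This reproduces the stated power. Read as an exact binomial test, success needs 70/116 (one-sided alpha 0.0161; 69/116 gives 0.0254), with power 87.4%. N, alpha and planned power do not depend on this point.

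**2. How often a partial diary settles the matter.** Assumptions: Poisson leaks, true baseline mean 12 per 72 hours, entry rule applied, 48 of 72 hours kept. The recorded count exceeds half of baseline with probability 0.68 if there is no true reduction, 0.38 to 0.39 with a true 30% reduction, and 0.18 with a true 50% reduction.

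**3. Diaries cut short at random.** Let f be the share of incomplete diaries that are proven failures, u the true responder rate in the undetermined rest, and p = (1 − f)u the overall rate. The model imputes everyone at p on average.

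- Overstatement from proven failures: f × p
- Understatement from the rest: (1 − f)(u − p) = p − (1 − f)p = f × p

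These cancel exactly. Two illustrative mixes of true improvement:

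| | f | u | p = (1 − f)u | f × p | (1 − f)(u − p) |
|---|---|---|---|---|---|
| Mix A | 0.18 | 0.81 | 0.664 | 0.12 | 0.12 |
| Mix B | 0.20 | 0.81 | 0.648 | 0.13 | 0.13 |

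The net bias is zero.

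**4. Incompleteness related to Month 6 leakage.** Assume proven failures are twice as likely to be incomplete. The true rate among incomplete diaries is then (1 − f)u/[(1 − f) + 2f] = p/(1 + f).

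- Mix A: 0.664/1.18 = 0.563, overstatement 0.664 − 0.563 = 0.10 per incomplete diary
- Mix B: 0.648/1.20 = 0.540, overstatement 0.648 − 0.540 = 0.11

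The complete diaries are now short of failures, which raises the imputed rate a little further. If, say, 10% of the others and 20% of proven failures are incomplete, mix B completers respond at 0.648 × 0.90/(1 − 0.12) = 0.663, and the overstatement is 0.663 − 0.540 = 0.12. Simulation gives 0.11 to 0.13 per incomplete diary. At N=116 that is 0.11/116 = 0.09 to 0.13/116 = 0.11 percentage points each. Ten incomplete diaries would add 1.1 to 1.3 responders, about 1 point.

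These figures assume that the earlier visits carry no information about Month 6. If they predict the loss of effect, the overstatement is smaller; if they point the wrong way, as with loss after Month 3, it is larger.

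**5. The extreme.** If every incomplete diary were a proven failure, each would add p/116, that is 0.43 points (p = 0.50) to 0.56 points (p = 0.65). At a true rate of 50%, the simulated one-sided rejection rate (Wald test with Rubin's rules) is about 0.026 with one such subject, 0.036 with three, 0.063 with five and 0.141 with ten. The same Wald test with no such subject gives about 0.025.

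**6. Scoring proven failures alone.** If the undetermined rest are still imputed as planned and truncation is random, the bias is −(1 − f)(u − p): −0.12 (mix A) to −0.13 (mix B) responder per incomplete diary. Simulation gives −0.12 to −0.16.

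**The case against.** The strongest objection is the cancellation in step 3: under the plan's own missing-at-random assumption, ignoring the partial diary does not inflate the responder rate. This stands. A reader might infer that the error runs one way, since a partial diary can prove failure but not success, and might then charge each proven failure at 0.56 points as bias. That counts only one half of a balanced error. Nothing in the documents says that incomplete diaries come mainly from failures, so the rejection rates in step 5 describe an extreme and not the plan's operating characteristics.

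Second, the wording leaves room. The primary-endpoint text speaks of data capture and not of diaries, bases the analysis on whatever data are available, and makes non-response depend on analyzable data. A partial diary could be scored under those words. But no rule says so. The primary endpoint is the diary, and Section 5.2.4.6.2 shows that incomplete diaries were foreseen. Section 5.2.3.1 points to a Section 11.4 that the supplied text does not contain; a completeness rule may stand there.

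Third, there are safeguards. Staff review each diary with the subject (Section 4.2.5), a check-in is planned at about 5 months (Section 4.1.6), and visits may be postponed for illness or interrupted stimulation (Section 4.1). These should keep the number of partial diaries small. The tipping-point analysis includes the case of all missing values as failures, which bounds the effect. It remains a sensitivity analysis, however, and it also lets proven failures count as responders.

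Fourth, the obvious remedy of adding average Month 6 leaks as a predictor fails: in complete diaries that variable and baseline together determine response, so the logistic model separates. The fix has to allow for this.

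**Conclusion.** The point holds as a defect of method. On the natural reading, the plan sets aside recorded outcome data and can impute a proven non-responder as a responder. Whether the rate is biased depends on why diaries are incomplete: no net bias if truncation is random, overstatement if it is related to Month 6 leakage beyond what the predictors capture. The documents do not establish which applies.

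The likely size is modest. At 0.11 to 0.13 responder per incomplete diary, it takes about eight or nine of them (1/0.13 = 7.7; 1/0.11 = 9.1) to add one responder. At the planning rate, 0.65 × 116 = 75.4 responders are expected against an exact cut-off of 70, so this would matter mainly for a result near the cut-off. The size rests on Poisson diaries with 48 of 72 hours kept, the assumed mixes, and the assumed doubling of incompleteness in proven failures. The number of incomplete diaries is unknown: the only loss figure in the sample size section, "Assuming an attrition rate of 20% between enrollment and the implant procedure", concerns the period before implant.

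**What to change.** Before the Month 6 analysis, define a complete diary and add both parts below to Section 5.2.4.6.1, ahead of the imputation steps.

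1. Score as a Treatment Non-responder any subject whose recorded Month 6 urgency leaks already exceed 50% of the 72-hour baseline count.
2. For incomplete diaries that remain undetermined, use the recorded Month 6 hours. Either impute the leak count for the missing hours and derive response from the total, or add to the logistic model the leaks over the recorded hours, computed over the matching hours in complete diaries so that the model is not separated.

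Part 1 must not be adopted alone, because it biases the rate downward (step 6 of the working). With both parts, simulation shows no bias whether truncation is random or related to Month 6 leakage.

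In Section 5.2.4.7, hold proven non-responders fixed, so that only undetermined outcomes are varied.

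The cost is a short addition to the text, some extra programming for matched hours or count imputation, and possibly a slightly lower responder rate. Sample size, alpha and planned power do not change.
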